5.3.2.2 Handling/Processing of Samples

The blood samples for adalimumab and AAA assays will be labeled with the type of sample, the protocol number, the subject number, the week and the assay type (pharmacokinetic [PK]-Adalimumab or AAA). Additional detailed instructions for the handling and processing of samples will be provided from the central laboratory.

5.3.2.3 Disposition of Samples

Frozen samples will be packed in dry ice (pellet form) sufficient to last 7 days during transport. Samples will be shipped by the central laboratory pursuant to instructions from the sponsor. An inventory of the samples will be included in the package for shipment.

5.3.2.4 Measurement Methods

Serum concentrations of adalimumab and AAA will be determined using a validated ligand binding assay (LBA) method under the supervision of the Bioanalysis Department at AbbVie.

5.3.3 Efficacy Variables

5.3.3.1 Primary Variable

The primary efficacy variable is the proportion of subjects achieving Clinical Response (remission and improvement) at Week 16.

For the efficacy assessment criteria, see [Appendix I](#).

5.3.3.2 Secondary Variables

Secondary efficacy variables, to be analyzed at each scheduled visit, include:

1. Proportion of subjects achieving Clinical Response (expect Week 16, which is the primary endpoint).
2. Proportion of subjects achieving remission.
3. Change from the Baseline in total GPP score (skin and systemic/laboratory test).
4. Change from the Baseline in JDA severity index of GPP.
5. Change and Percent change from the Baseline in total skin score.
6. Change from the Baseline in total systemic/laboratory test score.
7. Change from the Baseline in score of erythema area (overall) and BSA (BSA of GPP).
8. Change from the Baseline in score of erythema area with pustule and BSA.
9. Change from the Baseline in score of edema area and BSA.
10. Change from the Baseline in Body temperature.
11. Change from the Baseline in WBC.
12. Change from the Baseline in hs-CRP.
13. Change from the Baseline in serum Albumin.
14. Proportion of subjects achieving "Mild" in JDA severity index of GPP for patients with "Moderate" or "Severe" at the Baseline.
15. Proportion of subjects achieving Treatment Success in PGA (reduction of 2 grades).
16. Change from the Baseline in PGA grade.
17. Proportion of subjects achieving PGA 0/1 for patients with PGA grade at least 2 at Baseline.
18. Proportion of subjects achieving PASI 90.

19. Proportion of subjects achieving PASI 75.
20. Proportion of subjects achieving PASI 50.
21. Change and Percent change from the Baseline in PASI score.
22. Proportion of subjects achieving DLQI = 0.
23. Change from the Baseline in DLQI score.
24. Change from the Baseline in SF-36 score.
25. Proportion of subjects taking systemic co-medication for GPP (etretinate, MTX).
26. Proportion of subjects taking topical co-medication for GPP (corticosteroid, vitamin D3, tacrolimus).

5.3.3.3 Safety Variables

Safety will be assessed by adverse events, laboratory data and vital signs during the entire study period.

5.3.4 Pharmacokinetic Variables

Pharmacokinetic

Serum concentrations of adalimumab at each scheduled sampling time will be reported. Changes in serum adalimumab concentration in subjects who get dose-escalated will also be reported.

Immunogenicity

The number and percentage of subjects who develop AAA will be determined.

5.4 Removal of Subjects from Therapy or Assessment**5.4.1 Discontinuation of Individual Subjects**

A subject may withdraw from the study at any time. The Investigator may discontinue any subject's participation for any reason, including an adverse event, safety concerns or failure to comply with the protocol.

Subjects will be withdrawn from the study immediately if any one of the following occurs:

- Clinically significant abnormal laboratory result(s) or adverse event(s), as determined by the Investigator in consultation with the AbbVie SDP.
- The Investigator believes it is in the best interest of the subject.
- The subject requests withdrawal from the study.
- Inclusion and exclusion criteria violation was noted after the subject started study drug, when continuation of the study drug would place the subject at risk as determined by the AbbVie SDP (Section 5.2 and Section 7.0).
- Introduction of prohibited medications or dosages when continuation of the study drug would place the subject at risk as determined by the AbbVie SDP.
- Subject is non-compliant with TB prophylaxis.
- The subject becomes pregnant while on study medication.
- Subject has dysplasia of the gastrointestinal tract or a malignancy, except for localized non-melanoma skin cancer. Discontinuation for carcinoma in situ of the cervix is at the discretion of the Investigator.
- Subject is diagnosed with lupus-like syndrome, multiple sclerosis or demyelinating disease.
- Subject is significantly non-compliant with study procedures which would put the subject at risk for continued participation in the trial, as determined by the Investigator, in consultation with the AbbVie SDP.

If, during the course of study drug administration, the subject prematurely discontinues study drug use, the procedures outlined for the PD Visit must be completed within

2 weeks of the last dose of study drug, and preferably prior to the initiation of another therapy. However, these procedures should not interfere with the initiation of any new treatments or therapeutic modalities that the Investigator feels are necessary to treat the subject's condition. Following discontinuation of the study drug, the subject will be treated in accordance with the Investigator's best clinical judgment.

A final phone call will be made to the subject approximately 70 days after the last dose of study drug to determine the status of any ongoing AEs/SAEs or the occurrence of any new AEs/SAEs.

All attempts must be made to determine the date of the last dose of study drug and the primary reason for PD. The information will be recorded on the appropriate eCRF page.

For subjects that are considered lost to follow-up, reasonable attempts must be made to obtain information on the final status of the subject. At a minimum, two phone calls must be made and one certified letter must be sent.

5.4.2 Discontinuation of Entire Study

AbbVie may terminate this study prematurely, either in its entirety or at any study site, for reasonable cause provided that written notice is submitted in advance of the intended termination. The investigator may also terminate the study at his/her site for reasonable cause, after providing written notice to AbbVie in advance of the intended termination. Advance notice is not required by either party if the study is stopped due to safety concerns. If AbbVie terminates the study for safety reasons, AbbVie will immediately notify the investigator by telephone and subsequently provide written instructions for study termination.

5.5 Treatments

5.5.1 Treatments Administered

Subjects will receive adalimumab 80 mg (2 syringes) at Baseline (Week 0) by subcutaneous injection. At and after Week 2, subjects will receive 40 mg (1 syringe)

every other week (eow) subcutaneously until Week 50. No study drug administration will occur at Week 52.

Dose Escalation

For subjects who meet dose escalation criteria on or after Week 8, 80 mg (2 syringes) doses will be administered subcutaneously every other week until study end. No dose reduction will be allowed after dose escalation throughout the study. The dose escalation criteria are defined as the subjects who do not achieve Clinical Response (i.e., minimal improvement, unchanged or worsened) on or after Week 8 ([Appendix I](#)).

Prior to dose escalation, the observation result of skin lesions (GPP skin score, PGA and PASI score) will be recorded. Blood draw for the laboratory test (including WBC, hs-CRP and serum albumin for systemic/laboratory score) and measurement of pharmacokinetics and AAA will be also performed, prior to dose escalation.

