- m. Laboratory assessments will only need to be repeated at the Baseline if the time between blood sampling for Screening and Baseline is greater than 14 days, or if the subject's health status has changed to warrant a repeat test.
- n. Dipstick urinalysis will be conducted by the central laboratory at all required study visits. A microscopic analysis will be performed in the event the dipstick results show protein, ketones or blood greater than negative or glucose greater than normal.
- o. Subjects will be tested for HIV and documented that the test has been performed. This testing is to be done at the central laboratory. A subject will not be eligible for study participation if test results indicate a positive HIV infection. AbbVie will not receive results from the testing and not be made aware of any positive result.
- p. Subjects will be tested for the presence of the Hepatitis B Virus (HBV) at Screening. A positive result for the hepatitis B surface antigen (HBs Ag) will be exclusionary. Samples that are negative for HBs Ag will be tested for surface antibodies (HBs Ab) and core antibodies (HBc Ab Total). Subjects with HBs Ag (-), HBs Ab (-), and HBc Ab Total (+) require PCR qualitative testing for HBV DNA. Any HBV DNA PCR result that meets or exceeds detection sensitivity will be exclusionary.
- q. Anti-dsDNA will be measured if ANA is positive.
- r. Photographs of skin lesion will be taken at the time points above in subjects who agree to do in the pre-selected sites.
- s. When dose escalation is decided on unscheduled visit or on any visit when the data collection is not planned, the investigator must assess skin lesion (GPP skin score, BSA, PGA and PASI score), and perform blood sampling for laboratory test and PK/AAA prior to dose escalation. Body temperature will come from Vital Signs. Additional study drug dispense may be necessary, if appropriate.
- t. Administration of study drug will be performed after all assessments and examinations scheduled for that day have been completed. Study drug will be administered every other week in the investigator's office or at subject's home after training of self-injection to ensure proper technique.
- u. Blood samples for the measurement of adalimumab and AAA concentrations will be collected prior to dosing.

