5.6.4 Selection of Doses in the Study

Dose regimen was determined based on efficacy and safety data from the adult Ps population from Study M04-688, and observed long-term safety data from Ps study (Study M04-702) in Japan, according to the PMDA's advice.

Dose Escalation Criteria

When the enrolled subject would respond inappropriately during the course of the study, dose can be escalated to 80 mg eow on or after Week 8. The safety of 80 mg eow was confirmed in Studies M04-688/M04-702 Japanese Ps studies. The dose escalation criterion is when efficacy of subjects does not achieve the clinical response (i.e., minimal improvement, unchanged or worsened) at the time of evaluation. Time of dose escalation was justified from the result that the mean percentage change for the baseline in PASI score almost reached a steady state by Week 8 in Ps study.

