- o. Subjects will be tested for HIV and documented that the test has been performed. This testing is to be done at the central laboratory. A subject will not be eligible for study participation if test results indicate a positive HIV infection. AbbVie will not receive results from the testing and not be made aware of any positive result.
- p. Subjects will be tested for the presence of the Hepatitis B Virus (HBV) at Screening. A positive result for the hepatitis B surface antigen (HBs Ag) will be exclusionary. Samples that are negative for HBs Ag will be tested for surface antibodies (HBs Ab) and core antibodies (HBc Ab Total). Subjects with HBs Ag (-), HBs Ab (-), and HBc Ab Total (+) require PCR qualitative testing for HBV DNA. Any HBV DNA PCR result that meets or exceeds detection sensitivity will be exclusionary.
- q. Anti-dsDNA will be measured if ANA is positive.
- r. Photographs of skin lesion will be taken at the time points above in subjects who agree to do in the pre-selected sites.
- s. When dose escalation is decided on unscheduled visit or on any visit when the data collection is not planned, the investigator must assess skin lesion (GPP skin score, BSA, PGA and PASI score), and perform blood sampling for laboratory test and PK/AAA prior to dose escalation. Body temperature will come from Vital Signs. Additional study drug dispense may be necessary, if appropriate.
- t. Administration of study drug will be performed after all assessments and examinations scheduled for that day have been completed. Study drug will be administered every other week in the investigator's office or at subject's home after training of self-injection to ensure proper technique.
- u. Blood samples for the measurement of adalimumab and AAA concentrations will be collected prior to dosing.
- v. All AEs reported from the time of study drug administration until 70 days following discontinuation of study drug administration will be collected. SAEs and protocol-related nonserious AE will be collected from the time the subject signed the study-specific informed consent until 70 days following discontinuation of study drug administration.
- w. Site personnel will contact all subjects by phone 70 days after the last dose of study drug to determine the status of any ongoing AEs/SAEs or the occurrence of any new AE/SAEs.

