6.4 Definition of Analysis Windows

Since subjects do not always adhere to the study visit schedule, the following rules will be applied to assign actual visits to protocol-specified visits including early termination visits.

For each study visit mentioned in the protocol, a nominal or target day will be selected to represent the corresponding visit along with a window around the target day. Windows will be selected in a non-overlapping fashion so that a date collected on the CRF does not correspond to multiple visit windows. Moreover, windows will not discard any post baseline measurement recorded on the CRF. If a subject had two or more actual visits in one visit window, the visit closest to the target will be used as the study visit for that window. If two visits are equal distance from the target, then the later visit will be used for reporting.

The protocol specified visits and corresponding time windows used in the analyses are presented in Table 2, Table 3, Table 4 and Table 5.

The following visit windows will be used for the analysis of assessment of each efficacy variables which are collected at baseline visit and Week 52 Visit or early termination (ET).

Table 2.**Visit Windows for Analysis of Efficacy Variables, General Laboratory Parameters (Blood Chemistry and Hematology)**

Scheduled Week	Nominal Day	Time Window (Rx Day Range)
Day 1	1	≤ 1
Week 2	15	2 – 22
Week 4	29	23 – 43
Week 8	57	44 – 71
Week 12	85	72 – 99
Week 16	113	100 – 141
Week 24	169	142 – 211
Week 36	253	212 – 309
Week 52	365	310 – 421

Table 3.**Visit Windows for Analysis of DLQI, SF-36, Laboratory Parameters (Urinalysis)**

Scheduled Week	Nominal Day	Time Window (Rx Day Range)
Day 1	1	≤ 1
Week 8	57	2 – 85
Week 16	113	86 – 141
Week 24	169	142 – 211
Week 36	253	212 – 309
Week 52	365	310 – 421

Table 4. Visit Windows for Analysis of Vital Signs

Scheduled Week	Nominal Day	Time Window (Rx Day Range)
Day 1	1	≤ 1
Week 2	15	2 – 22
Week 4	29	23 – 43
Week 8	57	44 – 71
Week 12	85	72 – 99
Week 16	113	100 – 127
Week 20	141	128 – 155
Week 24	169	156 – 183
Week 28	197	184 – 211
Week 32	225	212 – 239
Week 36	253	240 – 267
Week 40	281	268 – 295
Week 44	309	296 – 323
Week 48	337	324 – 351
Week 52	365	352 – 379

Visit Windows for Dose Escalation Analysis Set

The study days for the analysis of dose escalation effect will be calculated with reference to the dose escalation date.

Study Day = Date of evaluation – date of dose escalation + 1.

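### A skin score required only because escalation for non-response was decided can replace the scheduled Week 16 score, which can turn a responder into a non-responder but not the reverse

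*Protocol*

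**What the plan says.** **When a skin score is required outside the schedule.** Footnote s to Protocol Table 1 reads: "When dose escalation is decided on unscheduled visit or on any visit when the data collection is not planned, the investigator must assess skin lesion". The same footnote appears under the SAP's study activities table (SAP 4.2), including the instruction to "perform blood sampling for laboratory test and PK/AAA prior to dose escalation". Protocol 5.5.1 fixes the order: "Prior to dose escalation, the observation result of skin lesions (GPP skin score, PGA and PASI score) will be recorded". That sentence covers every escalation and does not mention unscheduled visits; the link to unscheduled visits comes from footnote s.

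**What escalation means.** Protocol 5.5.1 and Appendix I allow escalation on or after Week 8 for subjects whose category is minimal improvement, unchanged or worsened. Protocol 5.6.4 says the criterion is met when the subject "does not achieve the clinical response (i.e., minimal improvement, unchanged or worsened) at the time of evaluation". These categories come from the same table that defines the primary endpoint (Protocol Appendix I, SAP 10.2 Table 6).

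**How a visit is chosen for analysis.** SAP 6.4: "If a subject had two or more actual visits in one visit window, the visit closest to the target will be used". A tie goes to the later visit. The section also says that "windows will not discard any post baseline measurement recorded on the CRF". Nothing in it excludes unscheduled visits or ranks scheduled ones first. The Week 16 window for efficacy variables (SAP Table 2) is Days 100-141 with target Day 113. Scheduled visits may be 7 days early or late.

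**The concern.** Closest-to-target is a sound rule when the existence of an extra measurement has nothing to do with its result. Here the result is the reason that the measurement exists. A subject who responds at the scheduled Week 16 visit and is worse some days later can acquire a second, non-responding score. A subject who does not respond at the scheduled visit and is better some days later has no required second score. The rule then chooses between recorded scores on date alone.

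At stake is the reported Week 16 Clinical Response rate, and Clinical Response in any other Table 2 window from Week 8 on into which such a visit falls. Whether a given subject is affected depends on which of two visits happened to lie nearer the target day.

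**Working it through.** **1. The plan's own figure, to locate the sensitive count.** SAP 4.3 states 82% power for an exact binomial test with n = 10, threshold 10%, expected 50%, one-sided 0.025.
- P(X ≥ 3 | 10, 0.1) = 0.070, which exceeds 0.025.
- P(X ≥ 4 | 10, 0.1) = 0.0128, so 4 responders is the critical count.
- P(X ≥ 4 | 10, 0.5) = 0.828, which agrees with the stated 82%.

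**2. Can displacement occur at Week 16?** The scheduled visit may fall on Days 106-120 (113 ± 7). For each such day, count the other days in 100-141 that are closer to 113, or equally close and later.

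| Scheduled day | 106 | 107 | 108 | 109 | 110 | 111 | 112 | 113 |
|---|---|---|---|---|---|---|---|---|
| Displacing days | 14 | 12 | 10 | 8 | 6 | 4 | 2 | 0 |

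| Scheduled day | 114 | 115 | 116 | 117 | 118 | 119 | 120 |
|---|---|---|---|---|---|---|---|
| Displacing days | 1 | 3 | 5 | 7 | 9 | 11 | 13 |

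The sums are 56 and 49, in total 105. The number of possible day pairs is 15 × (42 − 1) = 615, and 105/615 = 17.1%. This assumes that both visits are uniform over their ranges and that an unscheduled escalation visit does fall in the window. It counts displacement whatever the scheduled result was, so it is not a rate of changed results.

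Two cases:
- Scheduled Day 107 (6 days from target), response. Escalation visit Day 116 (3 days), non-response. Day 116 is used. Displacement by a later visit makes up 56 of the 105 pairs.
- Escalation visit Day 110 (3 days), non-response. Scheduled Day 118 (5 days), response. Day 110 is used, so a score taken before escalation replaces one taken after it, although SAP 5.1 analyses subjects regardless of escalation. Displacement by an earlier visit makes up the other 49 pairs.

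**3. Direction for the binary endpoint.** Take baseline skin scores 3-9 and scheduled and unscheduled scores 0-9, with the unscheduled score limited to those that meet the escalation criterion. Of 340 combinations, 152 turn a responder into a non-responder, 188 leave a non-responder unchanged, and 0 turn a non-responder into a responder. These are counts of possibilities, not probabilities. If the scheduled score is missing, non-responder imputation already gives non-response, so nothing offsets the loss.

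**4. Direction for the mean skin score.** In the same 340 combinations the unscheduled score is worse than the scheduled one in 229, equal in 34 and better in 77. An example of the last is baseline 8, scheduled 9, unscheduled 7. The effect on the mean is not one-way.

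**5. Effect of one displaced responder.** 1/10 = 10 percentage points. The exact 95% interval for 4/10 is 12.2% to 73.8%, and for 3/10 it is 6.7% to 65.2%.

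**6. Limit on exposure.** No dose reduction is allowed after escalation, so a subject escalates at most once and has at most one such score, in one window. If the day of an unscheduled escalation visit were uniform from Week 8 (Day 57) to the last dose at Week 50 (Day 351), the chance that it falls in the Week 16 window and displaces the scheduled score is about (42/295) × 0.171 = 2.4% per subject escalated at an unscheduled visit. That is before requiring a response at the scheduled visit. The uniform day is an assumption; the documents give no frequency.

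**The case against.** The strongest reply is that the event is rare and conservative. It needs an escalation decided at an unscheduled visit, in the right window, nearer to the target than the scheduled visit, with a response at one visit and non-response at the other within 14 days. The effect lowers the drug's response rate, so it cannot create a false claim of efficacy. SAP 10.1 defines no significance level for efficacy and calls for descriptive statistics with exact intervals. The 10% threshold appears only in the sample-size reasoning, so no success rule turns on 4/10 versus 3/10, and that pair is the most sensitive example. All of this stands. It limits the size of the point but does not remove it: the main product of a descriptive trial with 10 subjects is the estimate itself.

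A reader might also infer more than the documents support:
- *That no unscheduled score could help the drug.* Footnote s says what must be done when escalation is decided. It does not forbid a skin score at an unscheduled visit for another reason, and such a score could act either way.
- *That mean skin score, PGA, PASI and laboratory values are all biased toward worse.* Step 4 shows that the mean skin score can move either way. The other measures are not escalation criteria, and Protocol 5.3.1.1 allows extra laboratory tests when clinically warranted.
- *That Clinical Response is biased at every visit from Week 8.* Each subject can be affected in one window at most.
- *That 17% of Week 16 results would change.* The figure is conditional on the visit falling in the window and ignores the scheduled result.

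**Conclusion.** The point holds in a narrow form. Under the stated rules, an escalation score that the plan itself requires can replace the scheduled score in a Table 2 window. For binary Clinical Response, including the Week 16 primary endpoint, that replacement can lose a responder and cannot gain one. Each loss lowers the reported rate by 10 points with n = 10.

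This rests on the escalation criterion being judged on the score taken at that visit, as Protocol 5.6.4 says. Protocol 5.1 is looser and lists the three categories as examples of inadequate response. The 17% and 2.4% rest on uniform timing. How often escalation is decided at an unscheduled visit is unknown, and the effect is probably rare. This is a cheap improvement, best settled before database lock, and not a threat to the trial's conclusion.

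**What to change.** Add to SAP 6.4:

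> For by-visit efficacy analyses (Table 2), if the window contains a scheduled visit with a non-missing assessment, the scheduled visit closest to the target day is used (the later if tied). An assessment made at an unscheduled visit is used only if no scheduled assessment exists in the window. Assessments made at an unscheduled visit because escalation was decided remain the Day 1 value in the dose-escalation analysis (Table 5).

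The text must say which scheduled visit is meant, because Table 2 has no window for Weeks 20, 28, 32, 40, 44 or 48, and its wider windows can hold several scheduled visits. Table 5 already takes the escalation date as Day 1, so the escalation score keeps its purpose.

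The cost is a short SAP addition and a programming flag for scheduled versus unscheduled visits. The downside is that in a few cases a score nearer to the target day is set aside. With no scheduled assessment in the window, the escalation score would still enter the observed-case analysis as a non-response; under non-responder imputation it changes nothing. No clinical rule is touched.
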